within time correlations between mediator and outcome variables, longitudinal cross-lagged effects of mediator and outcome variables, effect of outcome at T0 on outcome at T2 and mediator at T0 on mediator at T2. In addition, we will test whether group (MBCT + TAU versus TAU) will have a significant differential effect on outcome at T2 (path a), on mediator at T1 (path b), and whether mediating variables at mid-treatment (T1) predict outcome post-treatment (T2). Finally, as a formal test of mediation, the indirect effect of group (MBCT + TAU versus TAU) on outcome at post-treatment (T2) via mediating variables at mid-treatment (T1) will be estimated using bootstrapping procedures (Selig & Preacher, 2009) consisting of 5000 bootstrap samples. We will calculate 95% confidence intervals (CI) of indirect effects (Preacher and Hayes, 2008). To separate within-person processes from stable between-person differences we will repeat the CLSEM models with the inclusion of random intercepts (Hamaker et al., 2015; Mulder & Hamaker, 2021), and compare results.

[figure not shown]

Figure 2. Structure of Cross-Lagged Structural Equation Models (CLSEM) of mediation for outcome at post-treatment (T2) by mediator at mid-treatment (T1). a represents the direct path of group on outcome, b the effect of group on mediator at mid-treatment, c the effect mediator of mid-treatment on outcome at post-treatment, while $b \times c$ represents the indirect path from group on outcome at post-treatment via mediator at mid-treatment. Note. Group = Mindfulness-based Cognitive Therapy (MBCT) + Treatment as usual (TAU) versus TAU, T0 = pre-treatment, T1 = mid-treatment, T2 = post-treatment.

As a sensitivity analysis we will perform a simple mediation analysis by using the PROCESS macro provided by Hayes et al. (2013). Group (MBCT + TAU versus TAU) will be entered as IV, pre- to post-treatment residualized change in depressive symptoms (IDS-SR) as DV, while pre- to mid-treatment residualized change in RNT/rumination (PTQ/RRS brooding subscale) will be entered as mediator. Other potential mediators of interest will be tested in an analogues manner.

Secondary outcomes: experimental tasks

1. Pavlovian to Instrumental Transfer Task

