Problems in motivation, reward and punishment processing and approach and avoidance behaviors have been central to cognitive-behavioral theories on depression (MDD) (see for reviews: Trew, 2011; Chen et al., 2015; Huys et al., 2015). The PIT paradigm therefore seems exceptionally suited to deliver rich behavioral information on the (individual variation of) affective-cognitive aspects relevant to depression in addition to for example questionnaire data. Indeed, two studies investigated PIT within MDD samples (Huys et al., 2016; Nord et al., 2018). Both studies find that MDD patients do not differ from healthy controls in the acquisition of instrumental contingencies (based on reward and punishment reinforcement learning) or Pavlovian contingencies (based on passive classical conditioning). However, in both studies the action specific PIT effect differs from HC, but in opposite directions: Nord et al. (2018) show that MDD patients show enhanced action-specific aversive PIT (i.e. the difference between the effect of an aversive CS on approach vs withdrawal actions), whereas Huys et al. (2016) show that MDD patients do show PIT in approach context, but that action-specificity is disturbed. Moreover, Nord et al. found a positive relation across (but not within) groups between depression symptom severity and action-specific aversive PIT, whereas Huys et al. found a negative relation between depression scores and action specific PIT within the patient sample. Moreover, Huys et al. found that action-specificity was related to improvement of depressive symptoms across 4-6 months.

Notably, explanation of these equivocal findings might contribute substantially to understanding the (cognitive-behavioral) variation within the heterogeneous MDD population. This might extend to the observed differences in populations recruited in these studies: Where Huys et al. included also MDD patients using psychotropic medication, Nord et al. did not. Here we set out to contribute to understanding these differences and extend our knowledge on PIT in MDD by addressing the following research questions:

- (1) First, we ask how, especially aversive, PIT differs between healthy controls, MDD patients with a current depressive episode or in remission.

(2) Second, within the MDD sample, we ask how depressive symptoms are related to PIT. We will explore the role of medication status on PIT in the MDD sample.

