(3) Third, we ask whether, especially action-specific aversive PIT is predictive of recovery of MDD in the currently depressed sample.

In addition, ample evidence shows that mindfulness-based cognitive therapy has beneficial effects for patients with MDD (Kuyken et al., 2016; Goldberg et al., 2019; Geurts et al., 2020). There are only some preliminary studies addressing the effect of mindfulness on PIT (Geurts et al., 2022a; Rosenthal et al., 2023). Geurts et al. (2022a) show that an 8 week MBCT course enhances aversive inhibition in patients with ADHD. Given the beneficial effect of MBCT on depression and a putative modulating role of MBCT on aversive Pavlovian inhibition we will assess whether MBCT indeed changes depressive symptoms in MDD patients compared to a waitlist control and how these changes are related to changes in PIT.

(4) Fourth, we will assess (a) what effect MBCT has on PIT in an MDD patient sample and (b) whether this relates to the change in depressive symptoms from pre-to-post MBCT.

Next to the main research questions, related to MDD and (the recovery of) depressive symptoms, we will assess on an exploratory basis the relation of PIT with rumination, based on the hypothesis that rumination is a consequence of lowered aversive PIT (cf. Huys et al., 2015) or increased active avoidance (Nord et al., 2018) and one of the proposed foci in the mode of action of MBCT.

Statistical analyses PIT

We will first perform an analysis to assess whether the data is better captured by a model that coded 3 valence levels (positive, neutral, negative, i.e. averaging across the high and low conditions within each Valence Context), or by a model that each of the 5 levels of Valence Context separately (cf. Huys et al., 2011b; Geurts et al., 2013b).

To assess the influence of motivational cues on instrumental behaviour, we will analyze invigoration (Go vs. NoGo responding) during Pavlovian to Instrumental transfer. To account for both

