between- and within-subject variability these data will be analysed with logistic mixed-level models using the lme4 package in R (Bates et al., 2014). Reflecting our objectives, the mixed models will include where appropriate the within-subject factors treatment (MBCT, waitlist), Action Context (approach vs. withdrawal) and Valence Context (appetitive/neutral/aversive), and the between-subject factors Group (HC, MDDremitted, MDDcurrent), medication status (serotonergic/catecholaminergic medication, no medication) and depressive symptom severity (in terms of IDS-SR score) or rumination (in terms of RRS brooding score). Models include all main effects and interactions. All models will contain a full random effects structure (Barr et al., 2013). When the full random effects structure prevents the models to converge, we will make amends.

Planned contrasts involve those contrasts focusing on action-specific aversive PIT, i.e. those interaction including an interaction between Valence Context (neu, aversive) x Action Context (approach, withdrawal). Next to the planned contrasts we will explore the full model. Thus, models relating to the different research questions will be:

(1) Valence Context * Action Context * Group + full random effects structure

MDD sample:

(2) Valence Context * Action Context * IDS-SR + random effects structure

(3) Valence Context * Action Context * IDS-SRchange + random effects structure

(4a) Time * Valence Context * Action Context * Treatment + random effects structure

(4b) Time * Valence Context * Action Context * Treatment * IDS-SRchange + random effects structure.

We will report effects significant at an alpha-level of $<.05$. Any significant higher order interactions will be analysed using post-hoc simple interactions for ease of interpretation.

Control analyses PIT

As sensitivity analyses we will conduct a number of control analyses that confirm the robustness of the results: we will assess the i) lack of effect of covariates of no interest, including age, gender, intelligence; ii) robustness of the results to exclusion of participants with deterministic PIT

responding; iii) successful instrumental conditioning, where we will also assess the influence of the degree of instrumental conditioning, and iv) Pavlovian conditioning on the main results.

[figure not shown]

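### PIT model 3 does not match research question 3: it covers a wider sample, leaves IDS-SRchange undefined and omits baseline IDS-SR and Treatment

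*SAP*

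**What the plan says.** The SAP section on PIT and depression poses the question as "3) Third, we ask whether, especially action-specific aversive PIT is predictive of recovery of MDD in the currently depressed sample". The section on statistical analyses of PIT then lists one model per question. For question 3 it gives "3) Valence Context * Action Context * IDS-SRchange + random effects structure".

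Models 2 to 4b share a heading that refers to the MDD sample without further restriction. The same section treats remitted and currently depressed patients as separate levels of a factor: "the between-subject factors Group (HC, MDDremitted, MDDcurrent". Treatment appears in models 4a and 4b but not in model 3. Baseline IDS-SR does not appear in model 3 either. The control analyses for PIT name age, gender and intelligence as covariates, and neither baseline severity nor arm.

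The PIT section does not say how IDS-SRchange is computed or over which interval, nor which PIT session enters model 3. In the mediation section, the sensitivity analysis names its outcome as "pre- to post-treatment residualized change in depressive symptoms (IDS-SR) as DV". The sample size section likewise speaks of residual change.

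**The concern.** Question 3 is about prognosis: does PIT tell us who recovers, beyond how ill the patient is at the start? A change score without its baseline cannot answer that cleanly. With similar variance before and after, a plain difference is negatively correlated with the starting value. Anything related to starting severity is then also related to change, whether or not it carries prognostic information.

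Whether PIT is related to severity is the SAP's own question 2: "within the MDD sample, we ask how depressive symptoms are related to PIT". If the answer is yes, models 2 and 3 could report the same cross-sectional association twice, the second time as prediction of recovery. Action-specific aversive PIT is a planned contrast and effects are reported at an alpha of 0.05, so a false finding would be presented as a result.

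Two further gaps are separate from this mechanism. The model's stated sample is wider than the question's. And if change is measured from T0 to T2, patients receiving MBCT and patients waiting are pooled without a term for arm, although the SAP's Design section has assignment follow clinical procedure and the start of treatment groups.

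**Working it through.** **Text comparison**

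| Item | Question 3 | Model 3 |
|---|---|---|
| Sample | currently depressed | MDD sample, no restriction |
| Target | recovery | IDS-SRchange, undefined |
| Baseline IDS-SR | – | absent |
| Treatment | – | absent (present in 4a and 4b) |

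The sentence before the list says "the mixed models will include where appropriate the within-subject factors treatment (MBCT, waitlist", but an explicit list follows it, and that list gives model 3 neither term.

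**Inputs for the illustration.** The SAP gives no figure for model 3, so there is nothing to reproduce. Its only sample size figure, 174, was set for the mediation analysis and serves here only as an illustrative N. Assumed, because the SAP gives neither:
- r, the correlation of PIT with baseline IDS-SR: 0 to 0.3
- rho, the pre-post correlation of IDS-SR: 0.4 to 0.8

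Also assumed: one linear PIT score per patient instead of the planned logistic mixed model, equal IDS-SR variance at both times, a two-sided 5% test, and no association of PIT with later IDS-SR given baseline.

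**Formula.** With unit variances and change = IDS2 − IDS0:
- cov(PIT, change) = r·rho − r = −r(1 − rho)
- var(change) = 2(1 − rho)
- corr(PIT, change) = −r·√((1 − rho)/2)

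For r = 0.3 and rho = 0.5 this is −0.3 × √0.25 = −0.15. By Fisher z at N = 174: atanh(0.15) × √171 = 0.1511 × 13.08 = 1.98. The rejection probability is about Φ(1.98 − 1.96), roughly 51%.

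**Simulated rejection rates without baseline IDS-SR** (4,000 samples per cell, N = 174):

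| r | rho 0.4 | 0.5 | 0.6 | 0.7 | 0.8 |
|---|---|---|---|---|---|
| 0 | 5.0% | 4.8% | 5.2% | 5.0% | 5.5% |
| 0.1 | 10.9% | 9.4% | 8.7% | 7.9% | 7.2% |
| 0.2 | 30.7% | 26.4% | 21.6% | 18.2% | 13.0% |
| 0.3 | 58.8% | 50.7% | 42.4% | 32.8% | 24.8% |

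With baseline IDS-SR in the model, the same cells give 4.5% to 5.7%. At N = 100 and r = 0.3 the rates are 15.6% to 38.4% without baseline and 4.2% to 5.4% with it.

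**Dependence on equal variances.** If the post-treatment SD is k times the baseline SD, the correlation is r(rho·k − 1)/√(1 + k² − 2·rho·k). For r = 0.3, rho = 0.5 and N = 170:
- k = 1: −0.150, rejection about 50%
- k = 1.2: −0.12/√1.24 = −0.108, about 29%
- k = 1.5: −0.075/√1.75 = −0.057, about 11%

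A post-treatment SD smaller than baseline moves the rate the other way.

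**The case against.** Several objections have force.

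- **The change score may not be a plain difference.** A reader might infer that the SAP specifies raw change. It does not; the term is undefined. Where the SAP does specify a change in depressive symptoms for modelling, it is residual or residualized. If IDS-SRchange is residualized on baseline, the artefact largely vanishes. This stands. What remains is that the natural reading of an unqualified change is a difference, and the SAP has to say which it is.
- **The plan does not predict a link between PIT and severity.** Question 2 is open, and the SAP describes the evidence as equivocal. Of the two cited studies in MDD, one found a relation across but not within groups; the other "found a negative relation between depression scores and action specific PIT within the patient sample". The link is therefore possible, not assumed by the plan, and its size is unknown. With r = 0 there is no inflation.
- **The sample heading may only separate models 2 to 4b from model 1,** which includes healthy controls, and question 3 already names the currently depressed. That is a fair reading of intent. The model list still does not carry the restriction, and one phrase would settle it.
- **Treatment may not be needed.** The only change window mentioned in the PIT section, under question 4, is pre to post MBCT, and the waitlist group later receives MBCT. On that window every analysed patient would have had MBCT. The need for a Treatment term therefore depends on the window, which is not given.

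**Conclusion.** The point holds in limited form. On the text alone, model 3 is listed for a wider sample than question 3, has no baseline IDS-SR or Treatment term, and uses a change score with no stated type or window. That model 3 can show a spurious prediction of recovery is conditional: it requires a plain difference and an association of PIT with baseline severity. The error rates illustrate that case under assumed r, rho, N and equal variances, in a linear analogue of the planned model. They are not estimates for this trial.

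Three stronger conclusions might be drawn, and the SAP does not support them:
- Including remitted patients does not demonstrably enlarge the artefact. A wider baseline range may raise rho as well as r, and a higher rho shrinks the induced correlation.
- Omitting Treatment does not create the baseline artefact. It is a separate matter of mixing arms and possible confounding.
- The calculation does not carry over to model 4b, which concerns PIT over Time, already contains Treatment, and was not examined here.

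This is a secondary task analysis and leaves the primary mediation analysis untouched. It should be corrected because a significant result would be read as prognostic.

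**What to change.** Amend the SAP's statistical analyses of PIT as follows:

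1. Restrict model 3 to MDDcurrent, as question 3 states.
2. State that PIT at T0 enters model 3.
3. Define IDS-SRchange: plain or residualized, and from which to which time point.
4. Add baseline IDS-SR, interacting with Valence Context × Action Context, so that the IDS-SRchange term is read given starting severity.
5. If the window is T0–T2 with both arms, add Treatment with the same interactions, because the arms receive different care and assignment follows clinical procedure.

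The cost is SAP wording: IDS-SR at T0 and group membership are already part of the plan's core data. The downside is a few more fixed effects and the smaller sample that question 3 already implies.

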Figure 3. Instrumental training. To centre the cursor, participants click in a central square. The experiment consists of a block with exclusively instrumental approach trials ($n=120$) and a block with exclusively withdrawal trials ($n=120$). In approach trials (top), participants chose whether to move the cursor towards the mushroom and click inside the blue frame onto the mushroom (go), or do nothing (nogo). In withdrawal trials, they instead moved the cursor away from the mushroom and clicked in the empty blue frame (go) or did nothing (nogo). Outcomes are presented immediately after go actions, or after 1.5 seconds. Per block there are 3 “good” and 3 “bad” instrumental stimuli. Participants play each block ones per testing day. Instrumental stimuli are different for both blocks and both days. **Pavlovian training.** Participants passively view stimuli and hear auditory tones, followed by wins and losses. There are five fractal/tone combinations. Each combination is displayed 12 times in the first block and another 6 times in the second block. **Pavlovian-instrumental transfer.** Participants respond to the instrumental stimuli trained during the instrumental training stage, with Pavlovian stimuli tiling the background. No outcomes are presented, but participants are instructed that their choices count towards the final total. No explicit instructions about the contribution of Pavlovian stimuli towards the final total are given.

2. The working memory update ignore emotion task (WMUIET)

The WMUIET (see Figure 4) contains black and white pictures of sad and neutral emotional faces. The task assesses the influence of emotional information on distractor resistance (ignore) and update capacity of working memory with (emotional) faces as target stimuli. Each trial contains three distinct phases separated by three delay periods.

First set of faces

Participants will be instructed to remember both the place of presentation and the face of two simultaneously presented black and white photographs when, and only when, the letter “T” (= target) appeared in the middle of the screen. Each presented set of photographs always contains two faces with the same emotion (neutral or sad).

Second set of faces

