In the second set, again two black and white pictures of faces will be presented. In total, there are four positions (top left/right, bottom left/right) and the first set always contains opposite positions compared to the second set, so that all four positions have shown a face once in every trial. In the second set, either a “T” or a “+” is presented in the middle of the screen. A “T” (= new Target) again indicates that this set of faces needs to be remembered (= update trial). A “+” (= distractor) indicates that the second set can be ignored (ignore trial). The participants are instructed that only the last target (“T”) set has to be remembered. Thus, the second set determines whether a trial consists of an ignore or update trial.

Probe phase

In the third phase, the probe phase, one face of the last target set is presented, and subjects will be asked to indicate at which position this face was presented in the last target-set with the D, K, C or M key on the laptop keyboard (see Figure 4).

No-interference (NI) trials - controls

In addition to normal ignore and update trials, the task also includes control, or so called no-interference, trials. In these trials, one of the representations does not consist of faces but of blank

rectangles. Therefore, only one set of faces is presented and should be remembered and there will be no influence of update or ignore functions of the working memory. In the update trials, the first set is blank, in the ignore trials the second set because these sets were not the final target sets in normal trials.

Possible combinations

Consequently, the task consists of 12 different types of trials. Four types of trials in both the ignore and update trials (sad → update: sad; sad → update: neutral; neutral → update: sad; neutral → update: neutral and sad → ignore: sad; sad → ignore: neutral; neutral → ignore: sad; neutral → ignore: neutral), two types of no interference ignore trials (neutral → blank; sad → blank) and two types of no interference update trials (blank → neutral; blank → sad). Each of these types consist of 20 trials, so there are 240 trials per participant.

Task variables

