Despite the demonstrated relationship between deficits in cognitive control over mood-congruent material and depressive rumination, the interplay with depressive symptoms is not well understood and no evidence is found for a direct relation with the influence of negative information in cognitive control (Everaert et al., 2017; LeMoult & Gotlib, 2019). Furthermore, most studies that investigate the effect of emotional valence on ignoring and updating of WM do not concomitantly measure and analyze the effects of both ignore and update processes within one task. A task measuring both processes will enable a more comprehensive analysis of the interacting relationship between updating and ignoring of the WM. More specifically, the influence of emotional valence on updating and ignoring processes in the WM, the interaction between those processes and the relation with clinical constructs such as rumination and depressive symptoms could be elucidated. It could be, for example, that ignoring and updating are reflections of the same disturbed mechanism with no additional value over each other in relation to clinical constructs. Alternatively, these processes might reflect different mechanisms that have additive explanatory value with respect to rumination and/or depressive symptoms. Recently, a new task has been developed to measure updating and ignoring of WM (Fallon & Cools, 2014; Fallon et al., 2017). For the current study, this task was extended with emotion manipulation to assess the emotion dependence of updating and ignoring, resulting in the Working Memory Update/Ignore Emotion Task (WMUIET). Our aim is to use this task to investigate whether

- (i) negative information influences task accuracy,
- (ii) depressive symptom severity (in terms of IDS-SR score) and/or rumination (brooding subscale of RRS) are correlated with updating and/or ignoring negative information in WM, and
- (iii) influence of negative information on ignoring and updating of WM is related to each other and have an interacting relation with other variables in patients with (remitting) persistent or recurrent MDD.

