We hypothesize that negative information in WM in MDD patients will attenuate updating based on the disengagement hypothesis (Koster et al., 2011; Southworth et al., 2017) and that MDD patients have more difficulty in ignoring negative information (less distractor resistance). Moreover, we hypothesize that MDD patients will show improved performance when asked to remember negative information. We expect these difficulties to be accompanied by increased rumination and we expect MBCT to normalize these findings.

Statistical Analysis WMUIET To answer our research question, we will employ generalized mixed effects models with correct choice as dependent variable. We will build the following models: (a) A model for the update trials; (b) a model for the Ignore trials; and (c) an omnibus model encompassing update and ignore trials to compare the relation between update and ignore processes. All models include the subjects as a random effect and will be constructed using a maximal fitting approach with random slopes and intercepts for all the non-correcting independent variables with more than one level (Barr, 2013; Barr et al., 2013).

Model (a) on update trials will include the within subject factors 'Emotion of first set' (2 levels: neutral/sad) and 'Emotion of second set' (2 levels: neutral/sad). Note that in this model the first set must be updated by the second set (thus the second set must be remembered) to come to a correct answer.

Model (b) on ignore trials will include the within subject factors 'Emotion of first set' (2 levels: neutral/sad) and 'Emotion of second set' (2 levels: neutral/sad). Note that in this model the second set must be ignored (thus the first set must be remembered) to come to a correct answer.

Moreover, when significant main effects of emotion for the second set for update trials and of the first set for ignore trials were found, we will assess whether these were indeed due to specifically the update or ignore process respectively by incorporating the no-interference trial and Type of Trial (no-interference/interference) as additional factor in the model.

Furthermore, to investigate the the within-subject relation between the update and ignore trials, an omnibus model will be constructed combining both update and ignore trials with the additional factor Type of Trial (Update/Ignore).

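### The WMUIET models have random effects for subjects only, so the test of target-set emotion leaves out differences between the face photographs that carry the emotion

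*SAP*

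**What the plan says.** All places are in the SAP.

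- **Model.** Statistical Analysis WMUIET plans "generalized mixed effects models with correct choice as dependent variable". On the random part it says "All models include the subjects as a random effect and will be constructed using a maximal fitting approach with random slopes and intercepts", the slopes being "for all the non-correcting independent variables with more than one level". Subject is the only grouping factor named.
- **Fixed effects.** Models (a) for update trials and (b) for ignore trials each contain the emotion of the first set and of the second set, at two levels. Model (c) combines both trial types. A significant emotion main effect for the second set in update trials, or for the first set in ignore trials, leads to a further model that brings in the no-interference trials.
- **Stimuli.** The task description says that the task "contains black and white pictures of sad and neutral emotional faces". Both faces in a set show the same emotion. Under Probe phase, "one face of the last target set is presented" and the participant reports its position.
- **Trial counts.** Possible combinations lists 12 trial types: "Each of these types consist of 20 trials, so there are 240 trials per participant".
- **Aim.** Aim (i), in the section on update and distractor resistance capacity in MDD, asks whether "negative information influences task accuracy".
- **Sensitivity analyses.** Control analyses WMUIET names age and gender. Nothing there concerns the stimuli.

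**The concern.** A given photograph is either sad or neutral, so photographs are nested within the factor under test. Some faces are easier to remember than others for reasons unrelated to emotion. The sad-minus-neutral contrast therefore contains a chance difference between the average memorability of the sad photographs and that of the neutral ones. Where participants see the same photographs, that difference is common to all of them. It then shifts the mean contrast without adding spread between participants, so by-subject slopes cannot absorb it. More participants shrink only the subject part of the standard error, so the omitted part weighs more as the sample grows.

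The exposed test is the main effect of target-set emotion, because the probe always comes from the target set: the second set in update trials and the first in ignore trials. These are the emotion main effects that open the no-interference follow-up, and they bear directly on aim (i). A significant result could reflect the photographs chosen rather than sadness.

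**Working it through.** **Plan's own figure.** 12 trial types × 20 = 240 trials, as stated. Each of models (a) and (b) uses 4 types × 20 = 80 interference trials. Two of the four types share each level of target-set emotion, giving 2 × 20 = 40 trials per level. The SAP gives no power or error-rate figure for this task.

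**Inputs.**
- From the SAP: 40 trials per emotion level; alpha 0.05, taken as two-sided.
- Assumed: N = 100 to 170 participants (for scale, the sample size section requires 174); accuracy 80%, so p(1 − p) = 0.16; by-subject emotion slope SD 0.3 logit; k = 10 to 40 photographs per emotion, the same for all participants; between-photo SD s = 0.1 to 0.3 logit; sad and neutral photographs independent.

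**Formulas (logit scale, true emotion effect zero).**
- Variance seen by the subjects-only model: V_sub = 2/(0.16 × N × 40) + 0.3²/N
- Variance left out: V_photo = 2s²/k
- Actual type I error: 2 × [1 − Φ(1.96 × √(V_sub/(V_sub + V_photo)))]

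**Worked case, N = 170, k = 20, s = 0.2.**
- V_sub = 2/1088 + 0.09/170 = 0.00184 + 0.00053 = 0.00237, so SE = 0.0487
- V_photo = 2 × 0.04/20 = 0.00400
- True SE = √0.00637 = 0.0798
- 1.96 × 0.0487/0.0798 = 1.195, so type I error = 23%

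**Ends of the range.**

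| N | k | s | V_sub | V_photo | Type I error |
|---|---|---|---|---|---|
| 100 | 40 | 0.1 | 0.00403 | 0.00050 | 6.5% |
| 170 | 20 | 0.2 | 0.00237 | 0.00400 | 23% |
| 170 | 10 | 0.3 | 0.00237 | 0.01800 | 50% |

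**Simulation check.** Trial-level binary data were generated with 2,000 replications per setting, mean logit 1.4, subject intercept SD 0.7 and slope SD 0.3. The subjects-only test was a one-sample t test on each participant's sad-minus-neutral accuracy, standing in for the random-slope model. Rejection rates at nominal 0.05:

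| N | Photos per emotion | s = 0 | 0.1 | 0.2 | 0.3 |
|---|---|---|---|---|---|
| 174 | 10 | 0.05 | 0.14 | 0.34 | 0.50 |
| 174 | 20 | 0.05 | 0.095 | 0.23 | 0.37 |
| 174 | 40 | 0.04 | 0.07 | 0.16 | 0.26 |
| 100 | 80, with 40 drawn per participant | 0.05 | 0.06 | 0.08 | 0.12 |

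The two approaches agree (23% against 0.23; 50% against 0.50). With no photo variance the test holds its level. A min-F′-type test that adds between-photo variance to the error term gave about 0.01 to 0.05 in every completed setting; it is conservative when photo variance is small. The crossed-intercept logistic model itself was not simulated.

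**A kinder design.** Suppose each person's face appears in both emotions and half the photo variance is shared within the person (an assumption). V_photo then halves. At N = 170, k = 20, s = 0.2: V_photo = 0.00200, 1.96 × √(0.00237/0.00437) = 1.443, type I error 15%. With k = 80 and s = 0.1 it is about 6%.

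**The case against.** The strongest reply is that the damaging conditions are not in the document. A reader might infer that one small set of photographs recurs for every participant. The SAP does not say so: it gives no pool size, reuse rule or method of assignment, and does not say whether one person's face appears in both emotions. Such task details may well stand in the protocol. This stands, and it makes the magnitude conditional. It does not repair the model, because the random structure is stated in the SAP and has no place for photo variance if any exists.

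A reader might also infer that every emotion test in this task is compromised. That goes too far, for three reasons.

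- **Non-target emotion.** The emotion of the set to be ignored or replaced is crossed with target emotion across the eight interference types. With balanced assignment, memorability of the probed face does not systematically produce an effect of non-target emotion, and the hypotheses on disengaging from and ignoring negative material are largely about that set.
- **No-interference trials.** The plan checks a significant target-set effect against these trials. If the same photographs serve in both, an easy face is easy in both, and its contribution largely cancels from the comparison. This partly protects the reading that an effect is specific to updating or ignoring. It does not protect the main effect behind aim (i) or the decision to open the follow-up.
- **Patient-level terms.** Interactions with Group, IDS-SR or brooding compare people who see the same photographs, so photo intercepts largely cancel.

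Finally, an intercept for the probed photograph cannot represent how distracting or how hard to displace the unprobed faces are. That is correct, and the fix allows for it.

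**Conclusion.** The point holds in a limited form. With subjects as the only grouping factor, the main effect of target-set emotion is tested against too small a standard error whenever photographs are shared across participants and differ in memorability. Aim (i) and the trigger for the no-interference follow-up depend on that test.

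The range of about 6.5% to 50% is illustrative. It rests on assumed values for the number of photographs, their SD, the number of participants, accuracy and the subject slope SD, and on independent sad and neutral photographs. The error comes close to 5% if photo variance is small or the pool is large, or if participants effectively receive different photographs. Redrawing from a moderate pool helps only in part: 80 photographs with 40 drawn per participant gave 0.06 to 0.12 for SD 0.1 to 0.3 at N = 100. The documents do not show that inflation of any particular size will occur.

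Nor do they support extending the point to the primary mediation analysis, which does not use this task. This is a worthwhile refinement to a secondary analysis.

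**What to change.** - Add a crossed random intercept for the probe face photograph to models (a), (b) and (c).
- State that if the random structure has to be simplified, this intercept is kept ahead of higher-order by-subject slopes.
- Where an effect of non-target-set emotion is interpreted, also include an item term for the non-target photographs.
- State the number of photographs per emotion and how they are assigned to trials and participants, so that a reader can judge the size of the issue.

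The change needs only the photograph's identity on each trial. If photographs hardly differ, the estimated variance goes to about zero and little is lost. The cost is somewhat wider intervals for emotion main effects and some extra convergence burden.
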